## 1. Protocol

The broad objective of our study was to examine the potential effect of Cannabidiol (CBD) on human learning and memory (L&M) in relatively small scale surveys, and with consideration of other confounding factors (i.e., other drugs being specifically combined with CBD or particular preexisting medical conditions). Our study design aimed to determine whether CBD, when administered alone to healthy human subjects is a modulator of human L&M. We also aimed to determine whether particular demographic factors present in the general population (e.g., age, sex, history of CBD use, and urine THC) would affect the modulatory effect of CBD on L&M.

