### a. Design and Participants

57 human volunteers were recruited from the Front Range communities in Colorado (Pueblo, Colorado Springs and Denver). Subjects were randomized to two treatment arms: 1) to receive CBD First; 2) to receive placebo first. Each applicant signed an informed consent form and filled out a demographics questionnaire. The L&M for each subject was tested after administration of 246 mg CBD absolutely or placebo. Testers were blinded as to whether someone is getting CBD or Placebo. The principal investigator remained unblinded, and was not be involved in data collection nor analysis to prevent any bias. Generation of the randomization list was performed by the principal investigator.

After administration of CBD or placebo the participants waited 2hrs before taking the learning and memory tests. The experiment was repeated one week later, by reversing the CBD and control groups, in order to eliminate (or minimize) the placebo effect.

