## 2. Statistical Analysis Plan

All statistical analyses were performed using SPSS. Linear Mixed Models (LMM) with Bonferroni Corrections were used to examine L&M scores of placebo and CBD recipients, while also controlling for demographic factors. Two-tailed  $P < 0.05$  will be considered statistically significant. Subject IDs were included as random effects. Treatment (CBD vs placebo) was included as a factor. The following were included as covariates: age, history of CBD use (user or non-user), sex (male or female), and urine THC result (THC positive or negative). A Linear Mixed model was created for each of the following dependent variables: MOCA, Sum of List A trials, List B, PI Ratio, RI Ratio, FS Ratio, and Total Prose Recall.

COVID as a factor was removed from the Linear Mixed Models. Data related to COVID will be independently analyzed in a separate statistical model and reported later.

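### The second aim, whether age, sex, CBD-use history and urine THC change the CBD effect, has no matching term or contrast in the planned models

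*Combined protocol and SAP*

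**What the plan says.** The opening paragraph of section 1 (Protocol) gives two aims. The first is whether CBD alone modulates learning and memory in healthy subjects. The second reads "We also aimed to determine whether particular demographic factors present in the general population (e.g., age, sex, history of CBD use, and urine THC"), and ends "would affect the modulatory effect of CBD on L&M". What the factors are to act on is the CBD effect, not the score itself.

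Section 2 (Statistical Analysis Plan) describes the models. Treatment is a factor, subject is a random effect, and the four variables have this role: "The following were included as covariates: age, history of CBD use (user or non-user), sex (male or female), and urine THC result". Their stated purpose is adjustment: "while also controlling for demographic factors". One model of this form is fitted to each of seven outcomes ("A Linear Mixed model was created for each of the following dependent variables").

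On the design, section 1a (Design and Participants) says "The experiment was repeated one week later, by reversing the CBD and control groups", so each subject is tested under both treatments.

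**The concern.** The second aim is a question of effect modification: is the CBD-placebo difference larger or smaller in, say, users than in non-users? The four variables in that aim are exactly the four covariates in the model, yet the model uses them only to describe score levels. No section names a treatment-by-factor product, a subgroup model, or a CBD-placebo contrast within levels of a factor.

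Two things are at stake. One of two stated aims would end without a result. And the only output tied to these factors would be the covariate coefficients, which a reader who knows the aim could easily take as evidence for or against modification.

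**Working it through.** **Inputs.** From the documents: 57 recruited and two test sessions one week apart (section 1a); seven outcomes, two-sided 0.05 (section 2). The plan contains no power, SD or sample-size figure to reproduce.

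Assumed: all 57 complete; 80% power; score SD of 1 in each session; within-subject correlation ρ of 0.7 or 0.5; factor splits of 28/29, 14/43 and 6/51; one urine THC status per subject; period modelled, or no period effect. Paired results below are for ρ = 0.7 / 0.5.

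**Step 1: what the listed model can estimate.** Code treatment t as 0 (placebo) or 1 (CBD) and let x be a factor that is constant within a subject. The listed model is

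y = μ + τt + βx + b + e,

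with b the subject effect. In a complete pair, CBD minus placebo is d = τ + (e₁ − e₀). Both x and b cancel, so the covariate neither changes the treatment contrast nor says anything about how it varies.

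If modification exists, the true model has a further term γtx. Then d = τ + γx + (e₁ − e₀), and the subject's mean score contains (β + γ/2)x. The second aim asks about γ. The listed model has no γ, and its covariate coefficient estimates the mixture β + γ/2.

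Simulation agrees:
- 200 crossover trials of 57 subjects, with a sex difference of 0 under placebo and 2 under CBD (residual SD 1) and no average CBD effect. The sex coefficient should be 0 + 2/2 = 1; its mean was 0.99. The treatment estimate averaged −0.03 and differed by at most 2 × 10⁻¹⁵ with and without the covariates. With a treatment-by-sex term added, the mean estimate was 2.01 against a true 2.

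**Step 2: how far the covariate test can mislead.** Proportion of simulated trials significant at 0.05, split 28/29 (20,000 trials for the first two rows):

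| True state | Covariate test | Interaction test |
|---|---|---|
| Level difference 0.8, γ = 0 | 90% / 92% | 5% |
| γ = 0.6, factor difference −0.3 on placebo and +0.3 on CBD | 5% | 82% / 61% |
| γ = 0.6, factor difference 0 on placebo and 0.6 on CBD | 22% / 25% | as above (depends on γ only) |

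**Step 3: what the missing terms could detect.** The variance of d is v = 2(1 − ρ) = 0.6 / 1.0. The interaction SE is √(v/n₁ + v/n₂), and the detectable interaction is (z for 1 − α/2, plus 0.842) × SE. For 28/29 at ρ = 0.7: √(0.6/28 + 0.6/29) = 0.205, and (1.960 + 0.842) × 0.205 = 0.57.

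| Split | SE | Detectable, α = 0.05 | Detectable, α = 0.05/28 |
|---|---|---|---|
| 28/29 | 0.205 / 0.265 | 0.57 / 0.74 | 0.81 / 1.05 |
| 14/43 | 0.238 / 0.308 | 0.67 / 0.86 | 0.95 / 1.22 |
| 6/51 | 0.334 / 0.432 | 0.94 / 1.21 | 1.33 / 1.71 |

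The average CBD effect, by comparison, needs 2.80 × √(v/57) = 0.29 / 0.37. If a period effect of 0.5 SD is left unmodelled with balanced sequences, v rises by 0.5² = 0.25 and the 28/29 values become 0.68 / 0.83.

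**Step 4: multiplicity.** Four factors × seven outcomes = 28 tests. Uncorrected at 0.05, 28 × 0.05 = 1.4 false positives are expected, and the chance of at least one is 1 − 0.95²⁸ = 0.76 if the tests are independent. Bonferroni over 28 gives 0.05/28 = 0.0018 each.

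**The case against.** The strongest objection is that section 2 is short and mostly in the past tense. It lists variables and roles, not an equation. SPSS mixed models accept factor-by-covariate products, and a two-level treatment factor needs no pairwise Bonferroni correction, so unlisted contrasts may have been run. That correction could equally refer to the seven outcomes, so it is weak evidence. What stands is a limit on the claim: it concerns the plan as written, not what was fitted.

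Other points stand as caveats:
- The 5% for the covariate test under modification belongs to a symmetric scenario. If the factor matters only under CBD, the figure is 22% / 25%. The covariate test still cannot tell that case from a plain level difference.
- The detectable values treat one factor at a time. With all four interactions in one model, correlation r between two factors multiplies the SE by 1/√(1 − r²): 5%, 15% or 40% more for r of 0.3, 0.5 or 0.7. At r = 0.5, 0.742 becomes 0.742 × 1.155 = 0.86. CBD history and urine THC could be related; the documents give no figure.
- The crossover makes the interactions estimable in principle, but a nearly empty level would leave a term uninformative. No prevalences are given.
- Age is continuous, so the split-based values do not apply to it. If urine THC was measured at each session and changed, the cancellation in step 1 is not exact for it.
- The missing period term is a separate matter. It enters here only because it affects precision.

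None of these supplies the absent analysis. Low precision is a reason for exploratory reporting or for dropping the aim, not for keeping an aim without an analysis.

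**Conclusion.** The concern holds. The stated aim is effect modification and the written analysis is adjustment, so no parameter of the listed models estimates or tests the second aim. This follows from the text and the algebra and needs none of the assumed figures. Those figures show that the covariate test is a poor substitute (significant in about nine trials in ten when there is a 0.8 SD level difference and no modification) and that the proper terms would find only fairly large differences. The detectable sizes are best cases.

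The point should be fixed but does not threaten the main result: the average CBD-placebo contrast is untouched.

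**What to change.** Choose one of two routes.

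1. **Analyse the aim.** For each of the seven outcomes, add treatment-by-age (age centred), treatment-by-sex, treatment-by-CBD-history and treatment-by-urine-THC terms, with a week 1 / week 2 period term in the same model. Report each interaction with its 95% CI, the CBD-placebo contrast within each level (for age, at stated ages), and the number of subjects per level. Rest any statement about modification on these terms alone. Label them exploratory, and post hoc if they are added after the analysis. Define the correction family: all 28 tests or a stated smaller set. State whether urine THC was measured once or at each session. If such terms were already fitted, say so and describe them.
2. **Reword the aim.** Limit it to adjustment for these factors and make no statement about modification.

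Route 1 costs extra model terms on data already collected, wide intervals and 28 further tests, and the terms cannot be called prespecified if added now. Route 2 costs one sentence and gives up the question.
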